Title: Effects of Malleo-Lok Stiffness on Lower Limb Mechanics

NCT Number: 04806100

Date: April 11, 2023

Study Protocol:

Purpose and Procedures:

The primary goal of this line of research is to understand the effects of ankle foot orthosis (AFO) stiffness on gait biomechanics and overall joint level stiffness. An improved understanding of the effects of stiffness on joint and limb mechanics will benefit the future prescription of AFOs.

The primary purpose of this research study is to determine if the stiffness of a commercially available ankle foot orthosis (Malleo-Lok, Bio-Mechanical Composites, Des Moines IA) impacts gait biomechanics and overall joint level stiffness. Previously published research suggests that AFO stiffness can affect gait biomechanics and patient preference. However, previous studies have focused on traditional posterior strut devices with the strut aligned in the frontal plane to allow sagittal plane deflection. The Malleo-Lok is a novel, low-profile carbon fiber device with two laterally positioned struts aligned in the sagittal plane. The proposed study will provide insight that can be used by certified prosthetists orthotists (CPOs), physical therapists, and physicians to select the device that bests meets their patients' needs.

The secondary purpose of this research study is to determine the within session repeatability of a novel approach for in-vivo AFO stiffness testing. AFO stiffness testing is typically performed using mechanical testing systems without accounting for the interaction of the individual and the device. The novel in-vivo AFO stiffness testing approach will be completed twice within the session to evaluate repeatability, and determine if the approach differentiates between NoBrace, compliant AFO, and stiff AFO conditions. Non-invasive, wireless, surface electromyography sensors and retroreflective markers will be placed on the participants lower limb to measure muscle activity and movement, respectively. Force plates embedded in the floor will be used to measure forces on the limb to calculate joint moments. Participants will be given visual feedback to minimize the effects of muscle activity on measured joint stiffness. Participants will stand and sit with their foot (side with the Malleo-Lok AFO) on the force plate embedded in the floor and bring their knee forward over their stationary foot to deflect the device while minimizing muscle activity.

In this study, lower limb stiffness and gait mechanics will be evaluated in healthy, able-bodied adult participants across three conditions; "NoBrace" where participants are asked to walk normally with no bracing, "Stiff" where participants are asked to walk while wearing a Malleo-Lok with stiff struts, "Compliant" where participants are asked to walk while wearing a Malleo-Lok with compliant struts. Testing will occur in a randomized order. Questionnaires will be used to quantify participants' pain and perceived comfort and smoothness during walking. A motion capture system will be used to evaluate walking biomechanics and overall ankle joint level stiffness, allowing for comparisons between conditions. Small reflective markers will be placed on the participant's skin and lower limb forces, and body motion will be assessed using computerized motion capture cameras and force plates in the floor. Muscle activity data will be collected using non-invasive wireless surface electromyography sensors.

Objectives and Specific Aims:

Aim 1: Determine the effect of Malleo-Lok stiffness on lower limb mechanics during gait.

Hypothesis 1.1: We hypothesize that increasing stiffness of the Malleo-Lok will result in decreased ankle range of motion and increased knee flexion during gait.

Hypothesis 1.2: We hypothesize that increasing Malleo-Lok stiffness will result in an earlier, faster center of pressure progression

Aim 2: Determine the effect of Malleo-Lok stiffness on overall joint level stiffness.

Hypothesis 2.1: We hypothesize that measured stiffness will progressively increase between the NoBrace, Compliant and Stiff conditions.

Aim 3. Determine the within-session reliability of a novel in-vivo weight bearing approach to evaluating AFO

stiffness.

Hypothesis 3.1: We expect the novel approach to demonstrate excellent within-session reliability.

Background and Significance:

A1) Ankle foot orthoses (AFOs) are medical devices often used to support the foot and ankle during daily activities. AFO device stiffness can influence the level of support provided and motion at the ankle. There is a general consensus that increasing AFO stiffness decreases overall ankle range of motion[1-3] noticeably reducing peak ankle dorsiflexion[1,2,4-7] and plantarflexion.[1,8] In addition to effects at the ankle, AFO stiffness has been found to affect the knee during gait, with increased stiffness generally resulting in increased knee flexion at initial contact[1] increased peak knee flexion during stance phase[1,3,8,9] and decreased peak knee extension.[1,4] However, previous studies have focused on traditional posterior strut devices with the strut aligned in the frontal plane to allow sagittal plane deflection. The effect of lower profile devices with laterally positioned struts are poorly understood. In this study we will determine if the Malleo-Lok, a novel carbon fiber brace utilizing lateral struts, produces similar effects, and determine the effect of device stiffness.

A2) Although AFO stiffness is known to influence overall device function for some design approaches[1] AFO stiffness has only been loosely measured in the clinical setting[1,10] and is often subjectively chosen for each patient based on certified prosthetist orthotist (CPO) knowledge and prior experience. Multiple research teams have developed and tested methods to quantify AFO stiffness.[11-20] These methods are typically best suited for a research facility and involve a custom mechanical testing system. The testing rigs usually clamp the foot plate of the AFO to a rigid platform and move the proximal cuff[11-15] to quantify AFO stiffness around the anatomic ankle joint center[11,14,19] or the device axis of rotation.[15] Although testing devices have successfully estimated AFO stiffness, they generally fail to take into account the interaction between the device and biological limb. One device was built for use in a clinical space to test AFO stiffness while the patient is wearing their AFO.[16] However, the footplate is once again secured to a rigid platform, which is then rotated about the estimated anatomic ankle joint center to determine the overall limb stiffness while wearing the AFO.[16] This approach does not include the vertical load on the limb that likely influences device-limb interaction during gait. In this study we are testing a novel approach to measuring AFO-limb stiffness about the biologic ankle joint center to better represent the effects of AFOs on limb stiffness during gait.

A3) AFO-limb stiffness testing will use the same motion capture system used to collect gait biomechanics. The ability to collect reliable gait data across sites has been previously demonstrated[21,22] and the same techniques will be applied to this measurement. Muscle activity will be measured using non-invasive surface electromyography sensors on the skin. AFO-limb stiffness will be measured twice during the testing session in order to determine within-session reliability of the novel AFO-limb stiffness testing procedures.

Inclusion Exclusion Criteria:

Patient Inclusion Criteria

- Between the ages of 18 and 45
- Healthy without current complaint of lower extremity pain, spine pain, open wounds or active infections, or medical or neuromusculoskeletal disorders that have limited their participation in work or exercise in the last 6 months
- Able to hop without pain
- Able to perform a full squat without pain
- Ability to speak and understand English

Patient Exclusion Criteria

- Diagnosed with a moderate or severe brain injury
- Lower extremity injury resulting in surgery or limiting function for greater than 6 weeks

- Injuries that would limit performance in this study
- History of recurrent ankle sprains or chronic ankle instability
- Diagnosed with a physical or psychological condition that would preclude functional testing (e.g. cardiac condition, clotting disorder, pulmonary condition)
- Uncorrected visual or hearing impairment(s)
- Require use of an assistive device
- Unhealed wounds (cuts/abrasions) that would prevent AFO use
- BMI > 35
- Pregnancy – Per participant self-report. Due to the expected small number of pregnant individuals, and resulting inability to account for its effect on resulting outcomes participants will be withdrawn from the study

Design and Methods:

We anticipate the study will be completed in one visit. The approximate time to complete study activities is 3-4 hours. Although we will attempt to collect all data in the specific order listed, the number of study activities completed and the specific order of completion will be dependent on participant, staff, and study equipment availability.

Potential participants will answer pre-screening questions as listed on the Pre-Screening Checklist over the phone before scheduling visit one, or in person during the first visit. If they meet all inclusion and exclusion criteria they will be consented to participate. Following consent, subjects will be screened using the post-screening checklist. If subjects fail to meet the inclusion or exclusion criteria, their participation will end at that point.

We will collect anthropometric and demographic information, have participants complete questionnaires concerning pain and comfort and smoothness, and use a motion capture system to investigate effects of ankle orthosis stiffness on gait biomechanics and joint level stiffness. Study participants will undergo an evaluation of characteristics relevant to device design, such as anthropometrics (height, weight, etc.), ankle joint stiffness, and pain, among other factors.

Each participant will be given time to accommodate to the brace prior to collection. Participants will then undergo testing in each study condition (Stiff, Compliant, NoBrace) to determine how orthosis stiffness affects gait biomechanics and overall joint stiffness. We will use well-established techniques to obtain a range of biomechanical data as individuals walk at self-selected and controlled speeds.

Personal/demographic and anthropometric information will be used to fully characterize the study participants. Demographic factors include characteristics that are independent of the health condition but can potentially influence physical performance and an individual's course of recovery. We will collect multiple variables that have been previously associated with outcomes, including race, ethnicity, and education to characterize the cohort. Anthropometric and demographic information, such as age, biological sex, height, weight, leg length, shoe type, shoe length and width will also be used to characterize the cohort.

Patient-reported outcomes questionnaires will be used to evaluate participant pain, comfort and smoothness. These patient-centric assessments will provide insight that can be used to interpret other study findings. We have used the selected measures in the target population and expect that they will effectively capture device-related outcomes.

Comfort and smoothness will be assessed using a modified version of the Socket Comfort Score, a reliable, valid, and sensitive measure of device fit and comfort.[23] These measures have been shown to effectively capture patient perception, are responsive to simple modifications to CDO device function, and will be applied in a manner consistent with a prior publication by the research team.[24] Comfort scores range from 0 = most

uncomfortable to 10 = most comfortable, and from 0 = least smooth to 10 = most smooth.[23]

Pain will be assessed using a standard 11-point numerical pain rating scale, in which 0 = no pain and 10 = worst pain imaginable, in a manner consistent with multiple other protocols.[25,26] Using this highly reliable approach, participants will be asked to rate their pain at the start of each session, and report their pain with movement in the device (if any) during each walking condition.

Ground reaction force and motion capture data will be used to evaluate the motion and loading of the lower limb and CDO devices as participants walk on a level walkway at self-selected speed and a controlled speed based on leg length.[21,27] Ground reaction force and motion capture data will be used to evaluate the motion and loading of the lower limb as participants walk on an over ground walkway at self-selected speed and a controlled speed based on leg length.[21,27] A minimum of three non-collinear reflective markers placed on the skin to minimize skin-bone movement will be used to determine kinematics for the segments of interest (foot, shank, thigh, pelvis, trunk, arms and head). A pointer wand with a rubber tip will be used to identify bony landmarks for segment coordinate system definition. Visual 3D software (C- Motion Inc.) will be used to calculate segment and joint angles and velocities. Force plates imbedded in the floor will capture ground reaction forces. Data from successful trials will be analyzed using Visual-3D software package (C-motion Inc., Germantown, MD).[21] The ability to collect reliable data across sites has been previously demonstrated.[22] Techniques established by [name] will be used to assess ankle peak dorsiflexion, joint moments, and power.[21] The movement of the center of pressure (COP), the weighted average location of all ground reaction forces, has been directly related to prosthetic and orthotic device design, function, and participant preference.[24,28-30] The peak velocity of the COP and the time to peak will be determined as a percentage of stance, in a manner consistent with prior work by the research team.[24]

Muscle activity will be measured using non-invasive surface electromyography sensors on the skin. A total of 8 EMG electrodes will be placed on the participant, with 4 on each leg to measure activation of the soleus, tibialis anterior, and medial gastrocnemius and peroneus longus. EMG data will be collected bilaterally in the lower limbs and during normal walking and during in-vivo ankle stiffness testing. Participants will be given visual feedback to minimize the effects of muscle activity on measured joint stiffness. Participants will stand and sit with their foot (side with the Malleo-Lok AFO) on the force plate embedded in the floor and bring their knee forward over their stationary foot to deflect the device while minimizing muscle activity.

Video recordings will be collected during walking trials. Recordings will include walking on the level over ground surface in each condition and at each walking speed. The camera will be positioned so the top of the field of view will be at the shoulders to minimize the likelihood of capturing the participants face, and the files will be stored securely as described in section X.4 and will only be available to members of the research team. Collection of video recordings is required during testing for quality control purposes. Video recordings will be removed from the video camera after being transferred to the secure network drive server and will be retained to facilitate future analysis consistent with "Data Storage for Future Use" section in the informed consent document.

Statistical Analysis Plan:

Analysis Methods:

There is one independent variable (IV) in this study, stiffness of the ankle brace (compliant and stiff). All the primary dependent variables (e.g. ankle moments, ankle range of motion, push-off power, ankle joint stiffness) will be evaluated using similar statistical approaches within each group. One-way repeated measure ANOVAs will be used to evaluate the effect of brace stiffness. Paired t-tests with Bonferroni-Holm correction will be used for post-hoc comparisons. Multiple trials will be collected for each condition during in-vivo ankle-CDO stiffness testing. Intraclass correlation coefficients and minimal detectable changes values will be calculated for in-vivo ankle-CDO stiffness between the average measurement for time point 1 and time point 2.

Power Analysis:

The number of participants proposed for this study are consistent with those from prior investigations by [name] related to AFO design. Thirteen participants was sufficient to detect differences associated with AFO stiffness in a recent study by [name] (PMID: 25193884). A total of 20 participants were included to adequately evaluate reliability in Aim 3.

Literature Cited:

21. Wilken, J.M., et al., Reliability and Minimal Detectable Change values for gait kinematics and kinetics in healthy adults. *Gait Posture*, 2012. 35(2): p. 301-7.
22. Kaufman, K., et al., Reliability of 3D gait data across multiple laboratories. *Gait Posture*, 2016. 49: p. 375-381.
23. Hanspal, R.S., K. Fisher, and R. Nieveen, Prosthetic socket fit comfort score. *Disabil Rehabil*, 2003. 25(22): p. 1278-80.

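### How the randomized condition order is generated is not stated and the analysis has no period term, so any drift over the session would cost precision and power

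*Combined protocol and SAP*

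**What the plan says.** The Purpose and Procedures section names three conditions (NoBrace, Stiff, Compliant) and states: "Testing will occur in a randomized order". This is the only rule on condition order. No sequence list, blocking, counterbalancing or Latin square is described.

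Design and Methods anticipates a single visit: "The approximate time to complete study activities is 3-4 hours". It adds that "the number of study activities completed and the specific order of completion will be dependent on participant, staff, and study equipment availability", and does not say whether the randomized condition order is exempt. It also says "Each participant will be given time to accommodate to the brace prior to collection", without giving a duration.

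In the Statistical Analysis Plan, Analysis Methods gives the model: "One-way repeated measure ANOVAs will be used to evaluate the effect of brace stiffness". The follow-up is: "Paired t-tests with Bonferroni-Holm correction will be used for post-hoc comparisons". Neither has a term for period, order or sequence. Power Analysis sets the size: "A total of 20 participants were included to adequately evaluate reliability in Aim 3".

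**The concern.** Hypotheses 1.1, 1.2 and 2.1 all rest on within-person differences between conditions measured one after another in one long session. Walking at two speeds and repeated ankle loading could produce change over time through fatigue, practice or loosening of the joint. A paired comparison removes differences between people, but not differences between early and late measurements in the same person.

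If the braces fall at different average positions, drift multiplied by that gap is carried into the Stiff-Compliant estimate. Even when the average positions agree, drift adds scatter to the paired differences, because some people wear Stiff first and others Compliant first. The design can control the first effect by balancing orders, and the analysis can control the second with a period term. As written, the plan states neither.

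**Working it through.** **The plan's own figure.** The documents give no figure for order balance or drift. The sample size of 20 cannot be reproduced, because no alpha, power, effect size, SD or target ICC is stated. For scale only, assuming two-sided alpha 0.05 and 80% power, a paired t-test with n = 20 detects d = 0.66, where d is in SDs of the paired difference.

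**Inputs.** From the documents: 3 conditions, hence 3! = 6 orders; 20 participants; a 3-4 hour visit; no period term. Assumed: independent, equally likely orders; linear drift of 0 to 1.0 SD of the paired difference per position; d = 0.66.

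**Step 1: position gap.** Over the six orders, Stiff position minus Compliant position is -2, -1, +1, +2 with probabilities 1/6, 1/3, 1/3, 1/6. The mean is 0 and the variance is (4 + 1 + 1 + 1 + 1 + 4)/6 = 2. For the mean over 20 people, SD = sqrt(2/20) = 0.316. Exact convolution over 20 people gives:

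- mean absolute gap: 0.25 position
- gap of at least 0.3: 39% of draws
- gap of at least 0.5: 13% of draws
- gap of at least 1.0: 0.2% of draws

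By simulation, some pair of the three conditions is at least 0.5 apart in 29% of draws. This bears on Hypothesis 2.1, which orders all three.

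If the whole visit were three equal slots of 60-80 minutes, a gap of 0.5 would be 30-40 minutes. That is an upper bound, since the visit includes other activities.

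**Step 2: effect of drift on the estimate.** With drift b per position and residual SD 1, the paired difference has variance 1 + 2b², so the SD of the estimate is sqrt((1 + 2b²)/20):

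- b = 0: sqrt(1/20) = 0.224
- b = 0.25: sqrt(1.125/20) = 0.237
- b = 0.5: sqrt(1.5/20) = 0.274
- b = 1.0: sqrt(3/20) = 0.387

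Simulation of the plain paired t-test with independent orders (60,000 trials per setting) agrees closely, and mean bias is 0 to within 0.001:

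| Drift per position (SD) | SD of estimate | Type I error | Power at d = 0.66 | Type I error when gap is at least 0.5 |
|---|---|---|---|---|
| 0 | 0.224 | 5.0% | 80% | 5% |
| 0.25 | 0.237 | 5.0% | 75% | 8% |
| 0.5 | 0.274 | 5.2% | 62% | 16% |
| 1.0 | 0.385 | 5.0% | 35% | 28% |

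**Step 3: what each remedy does, at drift 0.5.** Blocked here means three full sets of the six orders plus two people on distinct orders.

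| Orders | Analysis | Type I error | Power at d = 0.66 |
|---|---|---|---|
| Independent | plain paired t | 5.2% | 62% |
| Blocked | plain paired t | 2.0% | 64% |
| Independent | with position term | 5.0% | 78% |
| Blocked | with position term | 5.1% | 80% |

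Balancing shrinks the true error of the estimate, but the plain t-test still counts drift as noise, so it becomes conservative. With no drift, blocked orders plus a position term give 79.6% power, against 79.8% for independent orders and the plain test, so the remedy costs almost nothing if drift is absent.

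These runs used a linear position term (one degree of freedom). The three-level factor recommended below uses two and was not run separately.

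**Step 4: the last two people.** 20 = 3 × 6 + 2, so exact balance of position counts is impossible. With any two distinct leftover orders, the gap can reach (2 + 1)/20 = 0.15 (SD 0.089). With a mirror-image pair (A-B-C and C-B-A), the mean positions are (1 + 3)/2, (2 + 2)/2 and (3 + 1)/2, all equal to 2. The Stiff-Compliant gap is then zero and linear drift cancels. Under this scheme at drift 0.5, the plain paired t-test has type I error 1.7% and power 64%. With a period term, power is about 81% and type I error 5%.

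**The case against.** The strongest reply is that random order already does its job. Order varies between people, so drift is zero on average in the Stiff-Compliant contrast. It also enters the error term, which keeps type I error near 5% at every drift tested. That stands. A reader might infer that drift would systematically create or hide a stiffness effect; a randomized order does not support that reading. What remains is lost precision, plus error in an unlucky draw: with drift 0.5 and a gap of 0.5, the estimate shifts by 0.5 × 0.5 = 0.25 SD.

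Second, a reader might infer that the orders are unbalanced. The documents do not say so. The sentence on order fits blocked or counterbalanced lists equally well, and the position-gap figures apply only if orders are drawn independently. The defect is that the method is not stated.

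Third, no drift size is given. Participants are healthy adults aged 18 to 45 who can hop and squat without pain. They have time to get used to the brace, and the 3-4 hours covers all activities. Drift may be small; at 0.1 SD per position, power is 79%. This stands too, and limits how much weight the power figures can bear.

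Fourth, choosing restricted over simple randomization is partly a matter of preference. That is fair for the list alone, since most of the power gain comes from the period term. The missing period term is a fact of the written analysis, whatever the method of generating orders.

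**Conclusion.** The point holds as a cheap improvement in precision and reporting. The plan describes no balancing of condition order, and its analysis cannot remove drift. Under independent orders, the Stiff-Compliant position gap has SD 0.32, with half a position or more in about one draw in eight.

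Power at d = 0.66 would fall from 80% to about 75%, 62% or 35% for drift of 0.25, 0.5 or 1.0 SD per position. With balanced orders and a period term it stays near 80%. The type I error of 8% to 28% in the table applies only to draws with a large gap and must not be read as the trial's overall error rate.

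These results assume independent orders, linear drift common to all participants, two-sided alpha 0.05 and d = 0.66, none of which the documents give. If the orders are in fact balanced, the gap figures fall away, but the case for a period term remains.

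**What to change.** 1. **Purpose and Procedures.** State that the six condition orders are assigned from a pre-generated list in randomly permuted blocks of six, and that the last two of the 20 participants receive a randomly chosen mirror-image pair of orders. Three full blocks (18 people) place every condition equally often in each position and equally often directly after each other condition. The mirror pair keeps mean positions equal at 20.
2. **Analysis Methods.** Add period (position 1, 2, 3) as a within-person factor to the model, and take the Holm-adjusted condition comparisons from that model instead of plain paired t-tests. Balancing without this step is not enough: at drift 1.0 SD, the mirror-pair scheme with a plain paired t-test has power of about 26%, against 35% with independent orders.
3. **Design and Methods.** Record the order actually used for each participant, and state that the availability sentence does not override the assigned condition order.

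If orders have already been drawn, the period term can still be added wherever the order used was recorded. With independent orders it gives about 78% power at drift 0.5.

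The cost is one list to prepare and two degrees of freedom for period, with no extra participants, visits or procedures. Exact equality of mean positions needs all 20 to complete as assigned; after a dropout or a changed order, the period term handles the remaining imbalance.

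### The SAP defines its only factor with two levels (compliant, stiff) and omits NoBrace; as written, no test covers NoBrace against either brace, including the NoBrace-to-Compliant step of Hypothesis 2.1

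*Combined protocol and SAP*

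**What the plan says.** The SAP, under Analysis Methods, defines the factor: "There is one independent variable (IV) in this study, stiffness of the ankle brace (compliant and stiff". It then gives the omnibus test, "One-way repeated measure ANOVAs will be used to evaluate the effect of brace stiffness", and the follow-up, "Paired t-tests with Bonferroni-Holm correction will be used for post-hoc comparisons". It does not mention NoBrace, count the levels of the ANOVA or list the pairs to be compared.

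The protocol sections describe three conditions:

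- Purpose and Procedures, study conditions: "In this study, lower limb stiffness and gait mechanics will be evaluated in healthy, able-bodied adult participants across three conditions". The three are then named as NoBrace, Stiff and Compliant.
- Purpose and Procedures, secondary purpose: the in-vivo test is repeated in the session to assess repeatability and to "determine if the approach differentiates between NoBrace, compliant AFO, and stiff AFO conditions".
- Objectives and Specific Aims, Hypothesis 2.1: "We hypothesize that measured stiffness will progressively increase between the NoBrace, Compliant and Stiff conditions".
- Design and Methods: "Participants will then undergo testing in each study condition (Stiff, Compliant, NoBrace) to determine how orthosis stiffness affects gait biomechanics and overall joint stiffness".

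**The concern.** The factor definition is the only place where the SAP states what the ANOVA compares, and it leaves out one of the three conditions studied. That condition is the baseline of Hypothesis 2.1. The outcome of that hypothesis, ankle joint stiffness, is among the SAP's examples of primary dependent variables.

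An analyst who follows the sentence exactly would compare Compliant with Stiff and stop. Two stated aims would then have no planned test: that stiffness rises from NoBrace to Compliant, and that the in-vivo method tells an unbraced limb from a braced one. Any NoBrace comparison reported later would lie outside the plan as written, and its place in the multiplicity correction would not have been fixed beforehand.

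**Working it through.** **Inputs.** Two levels in the SAP's factor definition; three conditions in the protocol; n = 20 from Power Analysis. The documents give no alpha, sidedness, power, effect size or SD. A two-sided family alpha of 0.05 and 80% power are therefore assumptions, used only to size the cost of the fix.

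**The plan's own figure.** The 20 participants are justified by precedent (13 in an earlier study) and by the reliability aim. No calculation is shown, so 20 cannot be reproduced. It was not derived from these tests and does not depend on the number of levels.

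**Step 1: what each reading tests.** With k levels and n participants, the one-way repeated-measures ANOVA has k − 1 and (k − 1)(n − 1) degrees of freedom, and there are k(k − 1)/2 pairs.

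| | Two levels, as written | Three levels, as designed |
|---|---|---|
| Degrees of freedom | 1 and 1 × 19 = 19 | 2 and 2 × 19 = 38 |
| Pairs | 2 × 1/2 = 1 | 3 × 2/2 = 3 |
| Compliant vs Stiff | covered | covered |
| NoBrace vs Compliant | not covered | covered |
| NoBrace vs Stiff | not covered | covered |

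With two levels the ANOVA is the paired t-test, since F = t². On simulated data with n = 20, both F and t² were 3.664, and p was 0.0708 for both. Within a single outcome there is then no family of pairs for Holm to adjust.

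**Step 2: which hypotheses are affected.** Hypothesis 2.1 needs two steps, NoBrace to Compliant and Compliant to Stiff; the two-level reading tests only the second. Hypotheses 1.1 and 1.2 concern increasing Malleo-Lok stiffness, which the Compliant-Stiff contrast addresses on either reading.

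**Step 3: cost of three levels to the Compliant-Stiff test.** Holm compares the ordered p-values with 0.05/3 = 0.0167, 0.05/2 = 0.025 and 0.05. Paired-t power is the probability that a noncentral t with 19 degrees of freedom and noncentrality d√20 exceeds the two-sided critical value, where d is the mean paired difference divided by its SD. Solving for 80% power:

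| Threshold | Critical t (19 df) | Detectable d |
|---|---|---|
| 0.05 | 2.093 | 0.66 |
| 0.025 | 2.433 | 0.74 |
| 0.0167 | 2.625 | 0.78 |

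An effect with 80% power at 0.05 has 70% at 0.025 and 63% at 0.0167. The strictest threshold is the worst case under Holm, so 0.78 is an upper bound for this t-test, before any requirement that the omnibus F be significant.

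**Step 4: both steps of Hypothesis 2.1 together.** Showing both adjacent steps is harder than showing one. As an illustration only, assume independent condition errors, NoBrace one Compliant-Stiff step below Compliant, and Holm over three pairs without gating. At a Compliant-Stiff effect of 0.78 SD, simulated power for both steps is about 82% if the NoBrace error SD equals the others and about 48% if it is twice as large. At 0.66 SD it is about 60% and 30%. The documents give no SDs, so these figures show sensitivity and do not estimate this trial's power.

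**The case against.** The strongest reply is that this is a slip of drafting. The parenthesis describes the stiffness of a brace, and an unbraced limb has none to list. The SAP itself says that multiple in-vivo stiffness trials are taken in every condition, and the protocol defines the conditions as three. Motion capture is meant to measure "overall ankle joint level stiffness, allowing for comparisons between conditions". An ANOVA with Holm-corrected follow-up tests most naturally implies at least three levels.

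Most of this stands: three levels were probably intended. But that is an inference, and the one explicit statement of the levels contradicts it. Nothing elsewhere lists the levels of the ANOVA or the pairs.

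Some stronger readings are tempting, but the documents do not support them:

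- A reader might infer that NoBrace was deliberately excluded, or that the analyst has nothing to go on. The cues above point clearly to three levels.
- A reader might infer that the Holm step is empty throughout. That holds only for pairs within one outcome. The SAP has several primary variables, gait is measured at two speeds, and the SAP does not limit Holm to pairs within an outcome.
- A reader might infer that the contrasts must be tested whatever the omnibus F shows. The SAP calls them post-hoc and does not say whether they depend on F. Gating is a separate design choice, and correcting the omission does not require settling it one way.

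**Conclusion.** The point holds as an inconsistency to correct before analysis. Followed as written, the plan covers one of three pairwise contrasts and leaves NoBrace untested against either brace. The count of levels and pairs rests on the documents alone.

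The consequence is bounded. NoBrace data are collected on either reading, the Compliant-to-Stiff step and Hypotheses 1.1 and 1.2 remain testable, and the sample size is unaffected. It would be wrong to conclude that Aim 1 fails or that the trial cannot answer Hypothesis 2.1; the data will be there, and what is missing is a stated test.

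The power figures rest on an assumed two-sided family alpha of 0.05 and 80% power, and the 0.66 and 0.78 SD apply to one contrast only.

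**What to change.** Replace the factor sentence with: *There is one within-participant factor, brace condition, with three levels (NoBrace, Compliant, Stiff).*

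Then:

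- Run the repeated-measures ANOVA on three levels with a sphericity correction, which matters only once there are more than two levels.
- Name the Holm family, for each outcome and (for gait outcomes) each walking speed, as Compliant minus NoBrace, Stiff minus Compliant and Stiff minus NoBrace.
- Judge the steps of Hypothesis 2.1 from Compliant minus NoBrace and Stiff minus Compliant, not from the omnibus F alone. A significant F shows that the conditions differ somewhere; it does not show a progressive increase.

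The cost is SAP wording only, with no new data and no change in N. Compared with a single two-level test, Compliant-Stiff faces a threshold between 0.0167 and 0.05, with the loss of sensitivity shown in the working. Power to show both adjacent steps is lower than for one and depends on the NoBrace variance, so 0.78 SD should not be quoted as sufficient for Hypothesis 2.1 as a whole.
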